## 12.2. Relationship to Study Drug

An Investigator who is qualified in medicine must make the determination of relationship to the study drug for each AE (Unrelated, Possibly Related, Probably Related or Definitely Related).

The Investigator should decide whether, in his or her medical judgment, there is a reasonable possibility that the event may have been caused by the study drug. If no valid reason exists for suggesting a relationship, then the AE should be classified as “unrelated.” If there is any valid reason, even if undetermined, for suspecting a possible cause-and-effect relationship between the study drug and the occurrence of the AE, then the AE should be considered “related.”

If the relationship between the AE/SAE and the study drug is determined to be “possible” or “probable” the event will be considered to be related to the study drug for the purposes of expedited regulatory reporting.

### **12.3. Recording Adverse Events**

Adverse events spontaneously reported by the patient/subject and/or in response to an open question from the study personnel or revealed by observation will be recorded during the study at the investigational site. Clinically significant changes in laboratory values, BP, and heart rate/pulse also need to be reported as AEs. Disease -related events will be recorded as AEs if the events occur with greater frequency, severity or duration than expected. Information about AEs will be collected from the signing of consent form and followed until resolution or maximally up to 14 days after the End of Maintenance. Serious Adverse Event information will be collected from time of consent and followed until resolution. The AE term should be reported in standard medical terminology when possible. For each AE, the Investigator will evaluate and report the onset (date and time), resolution (date and time), intensity, causality, action taken, serious outcome (if applicable), and whether or not it caused the patient to discontinue the study.

Intensity will be assessed according to the following scale:

- Mild (awareness of sign or symptom, but easily tolerated)
- Moderate (discomfort sufficient to cause interference with normal activities)
- Severe (incapacitating, with inability to perform normal activities)

It is important to distinguish between serious and severe AEs. Severity is a measure of intensity whereas seriousness is defined by the criteria above. An AE of severe intensity may not be considered serious.

Should a pregnancy occur, it must be reported within 24 hrs of the first awareness of the event and recorded on Xeris' pregnancy form. Pregnancy in itself is not regarded as an AE unless there is a suspicion that a study drug may have interfered with the effectiveness of a contraceptive medication.

The outcome of all pregnancies (spontaneous miscarriage, elective termination, normal birth, or congenital abnormality) must be followed up and documented even if the patient was discontinued from the study.

All reports of congenital abnormalities/birth defects are SAEs. Spontaneous miscarriages should also be reported and handled as SAEs. Elective abortions without complications should not be handled as AEs.

### **12.4. Reporting Adverse Events**

Adverse events including SAEs will be reported for all subjects from the time of consent until the completion of the End of Maintenance Visit. AEs that are ongoing at the End of Maintenance

Visit will be recorded on the CRF and followed until resolution or maximally up to 14 days after the End of Maintenance Visit or ET Visit.

Any SAEs considered possibly or probably related to the study drug and discovered by the Investigator at any time after the study should be reported. All SAEs must be reported to Xeris within 24 hr of the first awareness of the event. The Investigator must complete, sign and date the SAE pages, verify the accuracy of the information recorded on the SAE pages with the corresponding source documents, and send a copy to Xeris via email to both [[contact]](mailto:[contact]) and [[contact]](mailto:[contact]).

Additional follow-up information, if required or available, should all be sent to Xeris via email to both [[contact]](mailto:[contact]) and [[contact]](mailto:[contact]) within 24 hrs of receipt and this should be completed on a follow-up SAE form and placed with the original SAE information and kept with the appropriate section of the eCRF and/or study file.

Xeris is responsible for notifying the relevant regulatory authorities of certain events. It is the Investigator's responsibility to notify the Institutional Review Board (IRB)/Independent Ethics Committee (IEC) of all SAEs that occur at his or her site. Investigators will also be notified of all unexpected, serious, drug-related events (7/15 Day Safety Reports) that occur during the clinical trial. Each site is responsible for notifying its IRB or IEC of these additional SAEs.

## **12.5. Adverse Event Reporting Requirements to Regulatory Authorities**

Adverse event reporting by the Sponsor, including suspected serious unexpected adverse reactions, will be carried out in accordance with applicable regulations.

An Investigator must notify the IRB/IEC of the occurrence of any SAE, in writing, as soon as is practicable and in accordance with local regulations. A copy of this notification must be provided to Xeris Pharmaceuticals or its designee.

In the event of an SAE that meets the criteria for expedited reporting, an SAE report will be prepared for submission to the FDA and any other applicable authorities by Xeris Pharmaceuticals or its designee.

## **12.6. Clinical Laboratory Abnormalities and Other Abnormal Assessments Reported as Adverse Events and Serious Adverse Events**

Abnormal laboratory findings (eg, serum chemistry, hematology, and urinalysis) or other abnormal assessments (eg, ECG and vital signs) per se are not reported as AEs. However, those abnormal findings that are deemed **clinically significant** by the Investigator and/or delegate or are associated with signs/symptoms must be recorded as AEs if they meet the definition of an AE (and recorded/reported as an SAE if they meet the criteria of being serious) as previously described. Clinically significant abnormal laboratory or other clinically significant abnormal findings that are detected after consent or that are present at Screening and worsen after consent are included as AEs (and SAEs if serious).

## 12.7. Subject Monitoring

Subjects will be monitored for AEs throughout the study by the CRU staff. The Investigator or designated sub-Investigator will be available during onsite drug administration. The Investigator or designated sub-Investigator will also be available (eg, “on call”) for the subject as needed.

Subjects will be advised to notify their health care professionals (eg, physician, dentist, and/or pharmacist) that they are participating in a clinical research study before taking any medicines or undergoing any medical procedure.

## 12.8. Other Safety Parameters

### 12.8.1. Subject Blood Volumes to be Drawn Over the Course of the Study

The approximate amount of blood drawn over the course of the study for each subject is presented below in [Table 6](#) and [Table 7](#).

**Table 6: Number and Volume of Blood Collections for Subjects Not Participating in Pharmacokinetic Substudy**

Sample Type	Volume Per Sample (mL)	Total Volume (mL)			
		Screening Period	Titration Period	Maintenance Period	ET
Clinical Chemistry	7.5	7.5	0	15	7.5
Free and total T4	2	2	6-24	10	2
TSH	3.5	3.5	10.5-42	17.5	3.5
Hematology	3	3	0	6	3
Serology	5	5	0	0	0
Cumulative Sample Volume	21	21	16.5-66	48.5	16
		Total Volume (mL) for Study through End of Maintenance Period:			
		86-135.5			

Abbreviations: ET= Early termination; mL = milliliter; TSH = thyroid-stimulating hormone, T4 = thyroxine

**Table 7: Number and Total Volume of Blood Collections for Subjects Participating in Pharmacokinetic Substudy**

Sample Type	Volume Per Sample (mL)	Total Volume (mL)			
		Screening Period	Titration Period	Maintenance Period	ET
Clinical Chemistry	7.5	7.5	0	15	7.5
Free and total T4	2	2	6-24	10	2
TSH	3.5	3.5	10.5-42	17.5	3.5
Hematology	3	3	0	6	3
Serology	5	5	0	0	0
Substudy PK	4	0	0	64	0
Cumulative Sample Volume	25	21	16.5-66	112.5	16
		Total Volume (mL) for Study through End of Maintenance Period:			
		150-199.5			

Abbreviations: ET= Early termination; mL = milliliter; PK = pharmacokinetic; TSH = thyroid-stimulating hormone, T4 = thyroxine

### 12.8.2. Physical Examination

Complete and abbreviated physical examinations will be performed by the Investigator or appropriately trained, delegated designee at the timepoints specified in the Schedule of Assessments ([Table 2](#)).

Complete physical examinations include general appearance, head, ears, eyes, nose, throat, dentition, thyroid, respiratory, cardiovascular, abdomen, skin, neurological, musculoskeletal, and lymph nodes.

Abbreviated physical examinations include head, ears, eyes, nose, throat, respiratory, cardiovascular, abdomen, skin, musculoskeletal, and lymph nodes and any pertinent system based on any prior findings.

### 12.8.3. Weight, Height, BMI

Body height (centimeters) and body weight (kilograms) will be measured at Screening and will be used to calculate BMI ( $\text{kg}/\text{m}^2$ ). Body weight and height will be obtained with the subject's shoes and jacket removed.

### 12.8.4. Vital Sign Measurements

Vital signs (systolic and diastolic BP, heart rate/pulse, respiratory rate, oral temperature) will be measured as described in the Schedule of Assessments ([Table 2](#)). Three readings of BP and heart rate/pulse should be taken at intervals of 1 to 2 minutes. The three readings of each will be recorded on the eCRF and assessed to determine eligibility for inclusion into the study and throughout the study (Section [8.1](#)).

Subjects should be resting for at least 10 minutes in a supine position prior to measurement of BP and heart rate/pulse. See [Table 3](#) for timing window allowances with respect to measurement collection. Where possible, assessments should be conducted in order of least invasive to most invasive (See Section [11.5](#) for details).

### 12.8.5. Electrocardiogram

12-lead ECGs are to be performed prior to vital signs with subjects in a supine position at least 10 minutes before the reading is taken. See [Table 3](#) for timing window allowances with respect to measurement collection.

All ECG tracings will be reviewed and assessed by the Investigator or designee. All potentially clinically significant automated ECG readings should be repeated within 5 minutes of the reading. If potentially clinically significant reading is confirmed, then the ECG will be sent to a local cardiologist for review.

### 12.8.6. Local Tolerability

Local tolerability will be assessed following SC injection as follows:

- The Investigator/qualified designee will use the Modified Draize Scale ([Appendix E](#)) to assess erythema and edema formation at the injection site at  $30\pm5$  minutes after injection of XP-8121. Note: If the Draize score is  $>1$  at 30 minutes, the subject will be discharged, and a follow up visit will be scheduled at 24 ( $\pm3$ ) hrs after injection in order for the Investigator or designee to complete an assessment of the injection site using the Modified Draize Scale.

- To assess injection site discomfort, subjects will complete an 11-point Numeric Rating Scale (NRS) questionnaire and an Injection Site Discomfort Description and Duration Questionnaire 10 ( $\pm 2$ ) minutes after injection of XP-8121 ([Appendix C](#)).

### 12.8.7. Clinical Safety Laboratory Assessments

Safety laboratory tests will be performed at the timepoints specified in the Schedule of Assessments ([Table 2](#)). Additional laboratory tests may be performed at other times, if deemed necessary by the Investigator. A repeat of the Screening visit laboratory assessments for clinical safety (hematology, chemistry, and urinalysis) may be permitted after consultation with the Medical Monitor.

The central laboratory will perform hematology, chemistry, and urinalysis tests. Blood and urine samples for hematology, chemistry, and urinalysis will be prepared using standard procedures. Laboratory panels are defined as listed in [Table 8](#).

**Table 8: Clinical Safety Laboratory Tests**

Hematology	Serum Chemistry	Urinalysis (Dipstick)	Virology

 
• Erythrocytes (red blood cells [RBC])
 
• Hematocrit
 
• Hemoglobin
 
• Leukocytes with differential (including eosinophils, neutrophils, basophils, monocytes, lymphocytes, and reticulocytes)
 
• Mean platelet volume
 
• Platelets
 
	
 
• ALT
 
• Albumin
 
• Alkaline phosphatase
 
• AST
 
• Bicarbonate
 
• Calcium
 
• Chloride
 
• Creatine kinase
 
• Creatinine
 
• Globulin
 
• Glucose (fasting laboratory assessments only)
 
• HbA1c
 
• Phosphate
 
• Potassium
 
• Sodium
 
• Thyroid-stimulating hormone
 
• T4
 
• Total and direct bilirubin
 
• Urate
 
• Urea
 
	
 
• Blood
 
• Glucose
 
• Ketones
 
• Leukocytes
 
• Nitrite
 
• pH
 
• Protein
 
• Specific gravity
 
• Total bilirubin
 
• Urobilinogen
 
• If abnormality is noted for protein, blood, nitrite or leukocyte esterase, a microscopic examination of RBC, white blood cell (WBC), bacteria, and casts will be performed
 
	
 
• Hepatitis C
 
• Hepatitis B
 
• HIV
 

Abnormalities in clinical laboratory tests that are considered clinically significant are to be recorded on the AE eCRF page. If laboratory values constitute part of an event that meets criteria defining it as serious, the event (and associated laboratory values) must be reported as an SAE (see Section [12.4](#)).

### 12.8.8. Urine Drug Screen

A urine drug screen will be performed at Screening and will include the following:

- Tetrahydrocannabinol

- Cocaine
- Amphetamines
- Barbiturates
- Benzodiazepines
- Opiates
- Methadone
- Methamphetamines
- Ecstasy (3,4-Methylenedioxymethamphetamine [MDMA])
- Phencyclidine

Repeat assessments may be performed in the event of a suspected false positive result.

If the results are positive for a benzodiazepine that is being taken as a prescribed concomitant medication, as defined and documented in accordance with Section 9.2, then the assessment would not have to be repeated.

#### **12.8.9. Pregnancy Testing**

A urine pregnancy test is to be performed all timepoints specified in the Schedules of Assessments (Table 2). If a urine pregnancy test returns a positive result, a serum pregnancy test must be performed in order to confirm the result. If confirmed positive, subjects should be withdrawn and pregnancy reported to Sponsor within 24 hr. See Section 12.3 for reporting requirements for pregnancies.

## 13. STATISTICS

Detailed methodology for PK descriptive and inferential statistical analyses of the data collected in this study will be documented in the Statistical Analysis Plan (SAP). This SAP will be used for both clinical parameters from the eCRF and the PK parameters derived from bioanalytical analysis data. Procedures outlined in the SAP will supersede protocol-specified statistical methods in the event of divergence.

Descriptive statistics will be used to summarize clinical and laboratory data. Continuous data will be represented by n (number of subjects), mean, median, standard deviation (SD), and range. Categorical variables will be presented by number and percentage of subjects (n [%]). Additional details of the testing procedures not included here, including handling of missing data, will be described in the SAP.

If not otherwise stated, baseline will be determined by the last evaluable assessment prior to dosing in each period. Measurement of specific baseline values will be described in the SAP.

### 13.1. Sample Size Determination

Assuming a between-subject coefficient of variation of 0.5 and a within-subject, between measurements correlation of 0.5, a sample size of 38 subjects will have 80% power to reject the null hypothesis that the dose conversion factor is less than 3.2X or more than 5X, in favor of the alternative hypothesis that the dose conversion factor is between 3.2X and 5X (in other words, within 80% and 125% of the proposed 4X conversion factor derived from PPK modeling). For the exploratory endpoint of TSQM-9, assuming a SD of differences of 20, a sample size of 34 subjects will have 80% power to detect a difference of 10 in means (domain scores range from 0 to 100) with a 5% two-sided significance level ( $\alpha=0.05$ ). Taking into consideration study non-completers and non-normalizers of TSH at study end, a total of 44 subjects will be enrolled.

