## 7.4. Dose Titration and Adjustment Criteria

### 7.4.1. Target XP-8121 Dose Definition and Calculation

Predicted geometric mean AUC at steady state for XP-8121 1200  $\mu$ g was similar to the predicted geometric mean AUC at steady state for Synthroid 300  $\mu$ g. Based on PK modeling, an XP-8121 SC weekly dose of 4 times the daily oral levothyroxine dose is estimated to provide similar exposure (AUC). Thus, the target weekly dose of XP-8121 SC (in  $\mu$ g) is calculated as the current daily oral levothyroxine dose (in  $\mu$ g) multiplied by 4 rounded up to the nearest 50  $\mu$ g.

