### 7.4.2. Titration Period

The XP-8121 SC initiation dose will correspond to 50% of the target weekly dose of XP-8121 SC (in  $\mu$ g). During the Titration Period, XP-8121 will be titrated at a rate intended to mitigate potential adverse effects of thyroid hormone excess, while avoiding prolonged under-replacement. The response to titration will be carefully monitored to avoid these effects.

During the Titration Period, XP-8121 will be titrated based on individual response to therapy (using blood fT4 trough concentration as a fast-response marker) at intervals no more frequent than every other week and in dosage increments corresponding to 25% of the target dose, up to a maximum of 125% of the target dose or 1500 µg (whichever is lower).

Operationally, each week subjects will return to the CRU for dosing and to have trough fT4 concentrations measured. Based on the fT4 concentration, the Titration Period will proceed as follows:

- If fT4 concentration is below or within normal range (study reference range: 0.78 to 1.42 ng/dL), and no signs/symptoms of thyroid hormones excess are present, the dose of XP-8121 SC will be increased by 25% of the target dose (eg, if fT4 concentration levels drawn at Week 2 of Titration Period are confirmed to be within the normal range at Week 3 of Titration Period, XP-8121 will be increased to 75% of the target weekly XP-8121 SC dose). If a drug-related AE is reported or if overdosage is a concern, the Investigator should consult with the Medical Monitor before up-titrating.
- If fT4 is in the normal range with presence of signs/symptoms of thyroid excess, then XP-8121 titration will occur at the discretion of the Investigator and in discussion with the Medical Monitor.
  - Signs/symptoms of thyroid excess have differing dynamics (ie, start and worsen at varying time and rates) and are non-specific when assessed individually. Therefore, clinical judgment is needed to interpret them in the scenario of acute response to changes in the replacement levothyroxine dose using XP-8121. Investigators should determine whether solicited symptom(s) or observed sign(s) warrant a presumptive determination of thyroid excess (or intolerance of replacement therapy). Such determination should be made conservatively, considering the potential impact of the signs/symptoms on the subject well-being during the subsequent Maintenance Period (See [Appendix B](#) for a list of positive signs/symptoms of thyroid excess).

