## 10.4. Study Drug Preparation

Procedures relating to study drug preparation and dispensing are outlined in the Pharmacy Manual.

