2.2 Study Design and Dose Range Rationale

The current study was designed, incorporating United States Food and Drug Administration (FDA) guidance, to provide information on weekly use of XP-8121 in stably treated subjects with hypothyroidism. XP-8121 is a ready-to-use, liquid formulation of levothyroxine sodium intended for SC administration once-weekly. The goals of the study are to determine safe starting doses, safe and feasible titration schedules, and the effective dose range of XP-8121, wherein effectiveness is determined by maintenance of normalized TSH. The oral to injected dose-conversion target was considered the primary objective and serves as the basis for hypothesis testing and sample size determination. Pharmacokinetics will also be characterized in a subset of subjects to determine any

differences from modeled chronic pharmacokinetic (PK) that used data from healthy volunteers. The findings from this study will inform a future clinical efficacy and safety demonstration.

This is a non-randomized, open-label, single arm, self-controlled study (i.e., subjects serve as their own controls based on baseline assessment of thyroid function). The design is appropriate because replacement of deficient T4 with levothyroxine is necessary and sufficient to treat hypothyroidism. A comparator is not necessary for an initial assessment of the ability of SC administered levothyroxine to maintain normalized TSH in stably treated subjects, as efficacy is not being established by this study. Blinding is not necessary since all subjects receive active therapy and there is no comparator. Furthermore, the primary outcome measure, TSH, is objective, and compliance (adherence) with therapy will be assessed.

The XP-8121 initiation dose will correspond to 50% of the target weekly dose of XP-8121 SC, which is defined, per study hypothesis, as the baseline daily oral levothyroxine dose (in μ g) multiplied by 4, rounded up to the nearest 50 μ g. The lowest dose to be studied is 100 μ g. The highest dose to be studied is 1500 μ g weekly, selected based on the known safety and toxicity profile of levothyroxine, published use of oral levothyroxine as a weekly dose regimen, and the observed and expected PK profile of XP-8121. This dose is not expected to result in overdosage using the proposed biweekly titration-to-target scheme with careful safety monitoring as described below.

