4.4 Sample Size Considerations

Assuming a between-subject coefficient of variation of 0.5 and a within-subject, between-measurements correlation of 0.5, a sample size of 38 subjects will have 80% power to reject the null hypothesis that the dose conversion factor is less than 3.2X or more than 5X, in favor of the alternative hypothesis that the dose conversion factor is between 3.2X and 5X (in other words, within 80% and 125% of the proposed 4X conversion factor derived from Population PK modeling). For the exploratory endpoint of the treatment satisfaction questionnaire for medication (TSQM-9), assuming a SD of differences of 20, a sample size of 34 subjects will have 80% power to detect a difference of 10 in means (domain scores range from 0 to 100) with a 5% two-sided significance level ($\alpha=0.05$). Taking into consideration non-completers and non-normalizers of TSH at study end, a total of 44 subjects will be enrolled.

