7. ANALYSIS SETS

Analysis Set	Definition	Used for Analyses
Safety Population	All subjects who received at least one dose of XP-8121.	Disposition, Demographics, Medical History, Disease History, Concomitant Medications, Deviations, Safety Analyses, Tolerability endpoints Secondary endpoints, Exploratory endpoints (except PK related endpoints)
Completer Population	All subjects who completed the Maintenance Period and exhibit normalized TSH throughout the Maintenance Period while on a stable dose for approximately 6 weeks. Subjects with a reduced dose at any point during the Maintenance Period will not be included.	Dose Conversion Factor analysis, Sensitivity analysis of Change from Baseline of Blood Thyroid Hormone Concentrations Secondary Endpoint
PK Population	All safety population subjects who participated in the PK sub-study, who do not have any major protocol deviations affecting the PK endpoints and for whom a sufficient number of samples is available to determine at least one PK parameter.	PK analyses

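### Do the sample-size inputs assume more spread in the dose ratio than the titration levels allow, so that the 80% power at 38 should be restated?

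*Protocol*

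**What the plan says.** Protocol 13.1, the synopsis and SAP 4.4 carry the same calculation. Protocol 13.1 words it as "coefficient of variation of 0.5 and a within-subject, between measurements correlation of 0.5, a sample size of 38 subjects will have 80% power". The aim is to show that the conversion factor lies between 3.2X and 5X, that is, within 80% to 125% of 4X. Enrolment is 44, to allow for non-completers and subjects without normalized TSH. SAP 2.2 says the dose-conversion target "serves as the basis for hypothesis testing and sample size determination".

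The dose rules are in other sections:

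- Protocol 7.4.1 sets the weekly target as the daily oral dose "multiplied by 4 rounded up to the nearest 50" µg.
- Protocol 7.4.2 starts at 50% of target and moves "in dosage increments corresponding to 25% of the target dose, up to a maximum of 125% of the target dose", or 1500 µg if lower.
- SAP 7 limits the Completer Population: "Subjects with a reduced dose at any point during the Maintenance Period will not be included".
- On dose preparation, Protocol 10.4 says only: "Procedures relating to study drug preparation and dispensing are outlined in the Pharmacy Manual".

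Neither document gives a source for the two variance inputs. Neither states the one-sided level of the test or the true ratio assumed for power.

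**The concern.** A CV of 0.5 for each dose with a correlation of 0.5 describes two measurements that are only moderately linked. Here the XP-8121 dose is computed from the oral dose, so the analysed ratio is nominally 2X, 3X, 4X or 5X. A variable confined to four values has a maximum spread, and the planning SD lies above that maximum at a true 4X. If so, 80% understates the power at 4X. The allowance for losses also looks too tight. The text leaves 44 − 38 = 6 subjects to lose, whereas the smaller SD would leave 15. That could matter because the primary analysis keeps only Completers with primary hypothyroidism.

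**Working it through.** **1. The plan's own figure.** Inputs from Protocol 13.1: CV 0.5, correlation 0.5, n = 38, limits 3.2X and 5X. Assumed because not stated: true ratio 4X, and two one-sided 5% tests (inferred from the 90% CI in Protocol 13.5.1.1).

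- Log variance of each dose: ln(1 + 0.5²) = 0.2231.
- SD of the log ratio, correlation on the log scale: √(2 × 0.2231 × (1 − 0.5)) = 0.472.
- SD of the log ratio, correlation on the raw scale: √(2 × 0.2231 − 2 × ln 1.125) = 0.459.
- Margin on the log scale: ±ln 1.25 = ±0.223.
- Exact power at n = 38: 80.5% at SD 0.459 and 77.5% at 0.472. The normal approximation at 0.472 gives 79.5%.
- 80% is first reached at n = 38 and n = 40 respectively.
- With one-sided 2.5% tests, power would be 66.2% or 61.9%, so 5% is evidently the level used.

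The stated 80% at 38 reproduces.

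**2. The largest SD at 4X.** A variable confined to the interval from a to b with mean m has variance of at most (b − m)(m − a). With a = ln 2, b = ln 5 and m = ln 4:

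√(ln 1.25 × ln 2) = √(0.2231 × 0.6931) = 0.393.

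This needs ln 1.25 / ln 2.5 = 24.4% of subjects at 2X, 75.6% at 5X and nobody between. Exact power at n = 38 is about 93%, and simulating that two-point mix gives 93.8%. The smallest n for 80% is 29 (81.8%; n = 28 gives 79.98%), hence 44 − 29 = 15 losses. If CV 0.5 is kept for both doses, the implied log-scale correlation is at least 1 − 0.393² / (2 × 0.2231) = 0.65.

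**3. The same bound at other means.**

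| Geometric mean | Largest SD, unrounded levels |
|---|---|
| 4X | 0.393 |
| 3.5X | √(ln(5/3.5) × ln(3.5/2)) = 0.447 |
| 3.2X | √(ln(5/3.2) × ln(3.2/2)) = 0.458 |
| Any mean (half at 2X, half at 5X) | ln 2.5 / 2 = 0.458 |

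The planning SD of 0.459 is therefore about the ceiling of the dose grid when the mean is left open.

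**4. Rounding.** Rounding the target up widens the range. An 88 µg daily dose gives 352 µg, rounded to 400 µg, or 4.55X. The documents give no oral-dose mix, so every mix below is an assumption. The bounds are at a geometric mean of 4X and power is at n = 38.

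| Assumed oral-dose mix | Largest SD | Power |
|---|---|---|
| Ten strengths, 50–200 µg, equal shares | 0.411 | 89.9% |
| 30% on 88 µg | 0.441 | 84.3% |
| Uniform 50–200 µg | 0.449 | 82.7% |
| 30% on 63 µg | 0.460 | 80.3% |

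These bounds need nobody at 75% or 100% of target. With at least 25% of subjects at those levels, the bounds are 0.341 unrounded, 0.361 (ten strengths), 0.403 (uniform) and 0.416 (30% on 63 µg), with power of 98.0%, 96.4%, 91.3% and 89.1%.

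**5. Power away from 4X**, at SD 0.393 and n = 38:

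| True ratio | 3.6X | 3.7X | 3.8X | 4X | 4.4X |
|---|---|---|---|---|---|
| Power | 57% | 72% | 84% | 93% | 63% |

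A small SD does not protect against this. Simulated shares of 15/25/35/25% across the four levels give 3.55X, SD 0.30 and 66% power. Shares of 0/5/5/90% give 4.82X, SD 0.12 and 59%. With 29 analysed subjects at SD 0.393, power is 72% at 3.8X and 73% at 4.2X, so the 15-loss allowance also holds only at 4X.

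**The case for a change.** The case for restating is reasonable. The endpoint drives the sample size, the inputs have no source, and they ignore a link between the two doses that the protocol itself creates. A primary analysis with, say, 32 subjects would be read as underpowered when at 4X it may not be. The correction is a few sentences, and Protocol 13 says that "Procedures outlined in the SAP will supersede protocol-specified statistical methods in the event of divergence", so the SAP could move first.

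What stands is that the 80% is conservative at a true 4X on the nominal levels, and that the reader must infer the test level and the true ratio. Both can be inferred, because the 90% CI and the 80% to 125% window lead to them and they reproduce the stated figure.

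The rest does not carry. Planning on a variance at the upper end of what is possible is ordinary caution when the mean ratio is the quantity being estimated. The 0.393 bound also assumes that no analysed subject is below 50% of target. The text names no lower level, but it does not rule one out either, and a 25% level would raise the bound at 4X to √(ln 4 × ln 1.25) = 0.556. Finally, changing SAP 4.4 alone would leave it and Protocol 13.1 giving different power for the same test until the next amendment.

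**Conclusion.** No change is needed. The stated power is correct for its inputs, and the inputs are cautious. At exactly 4X, with a floor of 2X and no rounding, the planning SD of 0.459 to 0.472 exceeds the possible maximum of 0.393, and power is about 93% against the 80% stated. With the mean left open the grid allows 0.458, and under one assumed oral-dose mix rounding alone reaches 0.460 at 4X. The surplus is therefore not assured, and it shrinks quickly as the true ratio leaves 4X.

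Restating the figure would alter no enrolment, procedure, model or conclusion. The analysis in SAP 9.5 estimates the ratio and its 90% CI from the data and does not use the planning SD. A single figure of 93% would be less informative than the present 80%, because power here depends mainly on a true ratio that nobody knows yet. Keeping the cautious statement is a fair trade-off. The unstated test level and true ratio are gaps that an analyst can fill from the text.
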